6.3.6. Handling of missing value for secondary judgement criteria

For secondary endpoints, all secondary judgement criteria requiring a difference calculation except WPAI (EASI, DLQI, EQVAS of EQ-5D-5L, the several VAS for measuring pruritus, pain or sleep loss, and the laboratory parameters) will be treated as follows:

- If they are completely missing or if more than 25% of items are missing for scores calculated from different assessments (EASI and DLQI) during the first visit, no imputation will be made and the participants will not be considered in any of the analyses.
- For scores calculated from different assessments (EASI and DLQI), if less than 25% of items are missing at the inclusion visit, this will be imputed by the value representing the patient's optimal state.
- If they are completely missing or if more than 25% of items are missing for scores calculated from different assessments (EASI and DLQI) at all visits except the first, no imputation will be made and the participant will not be included in any of the analyses.
- If they are completely missing or if more than 25% of items are missing for scores calculated from different assessments (EASI and DLQI) at the visit 9 for less than 10% of randomized patients, no imputation will be performed.
- If they are completely missing or if more than 25% of items are missing for scores calculated from different assessments (EASI and DLQI) at the visit 9 for more than 10% of randomized patients, but this score is entered for at least one visit between visit 2 and visit 8, the last available data will be used for the analysis of the secondary endpoint.
- For scores calculated from different assessments (EASI and DLQI), if less than 25% of items are missing and this item has been completed for a visit other than the inclusion visit, only the missing item will be imputed using the last available data to complete the score.

The secondary endpoint WPAI will be treated as follows:

• If it is completely missing or if more than 25% of items are missing during the first visit or the visit 9, no

imputation will be made and the participants will not be considered in any of the analyses.

- If less than 25% of items are missing and the missing items are item 1, 2, 3, 5 and/or 6, they will be imputed by the value representing the patient's optimal state.
- If less than 25% of items are missing and item 4 is one of the missing items, it will be imputed by 35 (result for item 2 + result for item 3) corresponding to statutory working hours in France minus the sum of hours missed. If this value is less than zero, it will be replaced by the value 0.

For qualitative secondary endpoints IGA and PaGa, their treatment will be different:

- If they are missing during all the visits after visit 1, no imputation will be made and the participants will not be considered in any of the analyses.
- If they are missing at the visit 9 for less than 10% of randomized patients, no imputation will be performed.
- If they are missing at the visit 9 for more than 10% of randomized patients, the last available dataset will be used for the analysis of the secondary endpoint.

The secondary qualitative criterion EQ-5D-5L will also be treated differently:

- If it is completely missing or if more than 25% of items are missing during the first visit, no imputation will be made and the participants will not be considered in any of the analyses.
- If less than 25% of items are missing at the inclusion visit, this will be imputed by the value representing the patient's optimal state.
- If it is completely missing or if more than 25% of items are missing during all the visits after visit 1, no imputation will be made and the participants will not be considered in any of the analyses.
- If it is completely missing or if more than 25% of items are missing at the visit 9 for less than 10% of randomized patients, no imputation will be performed.
- If it is completely missing or if more than 25% of items are missing at the visit 9 for more than 10% of randomized patients, the last available dataset will be used for the analysis of the secondary endpoint (the last available data for the items if less than 25% of items are missing or the last available data for the full score if more than 25% of items are missing).

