11.8. WORK PRODUCTIVITY AND ACTIVITY IMPAIRMENT QUESTIONNAIRE (AT BASELINE AND V9)

- WPAI achieved (qualitative parameter: "Yes", "No")
 - o If "No", why? (qualitative parameter in plain terms)
- WPAI outcomes in impairment percentages (quantitative parameter), with higher numbers indicating
 greater impairment and less productivity, i.e., worse outcomes. The outcomes are calculated from these
 data:

Questions	Modality
Q1 - Are you currently employed (working for pay)?	"No" (skip to question 6) "Yes"
Q2 - During the past seven days, how many hours did you miss from work because of your health problems?	Quantitative parameter
Q3 - During the past seven days, how many hours did you miss from work because of any other reason, such as vacation, holidays, time off to participate in this study?	Quantitative parameter
Q4 - During the past seven days, how many hours did you actually work?	Quantitative parameter (if 0, skip to question 6)
Q5 - During the past seven days, how much did health problems affect your productivity while you were working?	Quantitative parameter (from 0 to 10)
Q6 - During the past seven days, how much did health problems affect your ability to do your regular daily activities, other than work at a job?	Quantitative parameter (from 0 to 10)

- O Work time missed in percent (quantitative parameter) calculated as follows: $\frac{Q^2}{Q^2 + Q^4} * 100$
- Impairment while working due to health in percent (quantitative parameter) calculated as follows:
 Q5 * 10
- Overall work impairment due to health in percent (quantitative parameter) calculated as follows: $\frac{Q^2}{Q^2 + Q^4} + \left[\left(1 \frac{Q^2}{Q^2 + Q^4} \right) * \frac{Q^5}{10} \right] * 100$
- Activity impairment due to health in percent (quantitative parameter) calculated as follows: Q6 *
 10

11.9. PATIENT'S GLOBAL ASSESSMENT OF DISEASE SEVERITY (AT BASELINE, V3, V5, V7 AND V9)

- PaGa achieved (qualitative parameter: "Yes", "No")
 - o If "No", why? (qualitative parameter in plain terms)
- PaGa evaluation (qualitative parameter: "Clear", "Almost clear", "Mild", "Moderate", "Severe")
- PaGa binary evaluation (qualitative parameter: "Clearance or almost clearance", "From mild to severe")

11.10. VISUAL ANALOG SCALES OF PRURITUS, PAIN AND SLEEP LOSS (AT BASELINE, V3, V5, V7 AND V9)

- VAS for measuring pruritus achieved (qualitative parameter: "Yes", "No")
 - o If "No", why? (qualitative parameter in plain terms)
 - VAS for measuring pruritus in mm (quantitative parameter)

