13.2.3. Dermatology life quality index

Definition and derivation

The efficacy endpoint is the change in DLQI score from baseline to Week 16 (quantitative parameter). It is calculated as follows:

Missing data for this criterion will be imputed as described in section 6.3.6 for these analyses.

This score is then binarised according to the improvement from baseline, separating participants with an improvement of 4 or more from the others (qualitative parameter), which corresponds to the Minimal Clinically Important Difference (MCID) of the DLQI (16).

The DLQI score at the visit 9 is also used in binary form as described in section 11.6.

Analyses

Change in DLQI score from baseline to the visit 9 will be compared between Arm A and Arm B using an ANCOVA with an analysis similar to the primary endpoint.

The proportion of participants with an improvement of 4 or more at the visit 9 and the participants with a DLQI score of 0 or 1 at the visit 9 will be compared between Arm A and Arm B using a two-sided stratified CMH test controlling for that factor on which the randomization is stratified. These analyses will be similar to the previous IGA analysis.

13.2.4. 5-Level EQ-5D

Definition and derivation

The EQ-5D-5L questionnaire consists of two parts. The first with qualitative data, the second (EQ-VAS) with quantitative data.

On the first part, the 5 components of the EQ5D-5L will be evaluated for each component by comparing the changes between the baseline results and the results at the visit 9 (qualitative parameter). Changes will be categorized in relation to the baseline, as described in the form associated with the questionnaire (2):

- Their health status (for the respective component) is better
- Their health status has worsened
- Their health status remains the same

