13.2.5. Work productivity and activity impairment questionnaire

Each WPAI outcome, described in section 11.8 (work time missed, impairment while working due to health, overall work impairment due to health and activity impairment due to health) will be analyzed independently but using the same procedure.

Definition and derivation

The efficacy endpoints are the change in WPAI outcomes from baseline to Week 16 (quantitative parameter in percent). It is calculated as follows:

WPAI outcome at visit 9 – WPAI outcome at visit 1

Missing data for this criterion will be imputed as described in section 6.3.6 for these analyses.

Analyses

Change in WPAI outcomes from baseline to the visit 9 will be compared between Arm A and Arm B using an ANCOVA with an analysis similar to the primary endpoint.

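### A single WPAI item left blank at visit 9 is entered as no impairment, because the 25% rule counts the whole form while the outcomes are analysed one by one

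*SAP*

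**What the plan says.** **WPAI, handling of blanks (SAP 6.3.6).** The first bullet is an exclusion: "If it is completely missing or if more than 25% of items are missing during the first visit or the visit 9, no" imputation is made and the patient leaves every WPAI analysis. The next covers forms with less than 25% of items blank: where "the missing items are item 1, 2, 3, 5 and/or 6, they will be imputed by the value representing" the patient's best state. It names no visit. Item 4 has its own rule, based on a 35-hour week.

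**WPAI, outcomes (SAP 11.8 and 13.2.5).** There is no sum score. Four percentages are derived:
- work time missed, from Q2 and Q4
- impairment while working, Q5 × 10
- overall work impairment, from Q2, Q4 and Q5
- activity impairment: "Activity impairment due to health in percent (quantitative parameter) calculated as follows: Q6" times 10

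Each "will be analyzed independently but using the same procedure", an ANCOVA of the change from baseline modelled on the primary analysis.

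**EQ-5D-5L (SAP 6.3.6 and 13.2.4).** "If less than 25% of items are missing at the inclusion visit, this will be imputed by the value representing" the best state. At visit 9 the rule differs: last available data if more than 10% of randomized patients are affected, otherwise no imputation. In the analysis, "the 5 components of the EQ5D-5L will be evaluated for each component by comparing the changes between the baseline results" and those at visit 9. An overall summary (Better, Worse, Exactly the same, Mixed) is then reduced to Improvement or No improvement, and only Better counts as Improvement.

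**The concern.** A tolerance for a few missing items makes sense for a summed score, where one filled-in item moves the total a little. It gives no protection when the outcome is one item. A blank Q5 or Q6 leaves nothing of that outcome observed, yet it passes a test meant to ensure that most of the information is there, and it receives the most favourable value on the scale.

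At visit 9 this creates a false full recovery. If blanks are equally common in both arms, the treatment difference shrinks and noise is added. If they are not, a difference appears that no patient reported. Work productivity and quality of life are stated secondary objectives (SAP section 4). The sensitivity analyses in 13.1.3 are specified for the primary endpoint only, so nothing planned would expose the distortion.

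**Working it through.** **Inputs from the SAP.** WPAI has 6 items (11.8) and EQ-5D-5L has 5 dimensions (11.7). The threshold is 25% of items (6.3.6). The sample size is 42 evaluable per arm and 94 randomized, so 47 per arm (5.3). The SAP gives no figure for item-level blanks. Its sample size is not in question and reproduces: t-test power is 80.8% at 42 per arm, difference 25 and SD 40, and 84/0.9 = 93.3, rounded up to 94.

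**Step 1: what passes the threshold.**

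| Form | 1 blank | 2 blank |
|---|---|---|
| WPAI | 1/6 = 16.7%, imputed | 2/6 = 33.3%, excluded |
| EQ-5D-5L | 1/5 = 20.0%, imputed at inclusion | 2/5 = 40.0%, excluded |

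So on either form exactly one blank item can be filled with the best value.

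**Step 2: what that item means for each WPAI outcome.**
- Q6 blank: activity impairment is 1/1 = 100% missing and is entered as 0 × 10 = 0%.
- Q5 blank: impairment while working is 100% missing and is entered as 0%. Overall work impairment loses its Q5 term.
- Q2 blank: work time missed becomes 0/(0 + Q4) = 0%, and overall work impairment is altered with it.

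**Step 3: effect on one patient and on an arm mean.** With Q6 = 7 at baseline and blank at visit 9, the recorded change is 0 − 70 = −70 points. If the unseen visit-9 value is t, one blank shifts the mean of a 47-patient arm by −t/47. For t from 20 to 60 (assumed) that is −0.4 to −1.3 points. Five blanks shift it by −2.1 to −6.4 points.

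**Step 4: effect on the comparison (illustration).** Assumptions: 42 per arm; baseline mean 55, SD 25, correlation 0.4; visit-9 means 40 and 25; scores in steps of 10 held within 0 to 100; blanks unrelated to the score; ANCOVA of change on arm and baseline; 4000 replicates. If a share r is blank in both arms, the difference is multiplied by (1 − r). If the shares differ and both arms have mean m, the false difference is −(r_dupilumab − r_placebo) × m.

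| Blank at visit 9 | By formula | Simulated, best value entered | Simulated, left missing |
|---|---|---|---|
| 10% in both arms | 0.9 × (−13.4) = −12.1 | −12.0, power 67% | −13.4, power 77% |
| 10% vs 2%, no true effect, m = 40 | −0.08 × 40 = −3.2 | −3.2, type I error 9.4% | – |
| 5% vs 2%, no true effect, m = 40 | −0.03 × 40 = −1.2 | −1.2, type I error 5.8% | – |

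Simulation error around a 5% rate is about 1.96 × √(0.05 × 0.95/4000) = 0.7 percentage points, so the last row is close to nominal.

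**Step 5: blanks at baseline only.** In the same setting, 5% blank at baseline gives power of 79.7% either way. At 10% it is 79.6% with the best value entered and 77.2% if left missing.

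**Step 6: EQ-5D-5L at inclusion.** From an imputed Level 1, visit-9 Level 1 reads as the same and Levels 2 to 5 read as worse; better is impossible. If another dimension improved, none worsened, and the blank dimension is at Level 2 or above at visit 9, the patient is classed Mixed, hence No improvement, even if that dimension had truly improved.

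**The case against.** Much of the case on the other side stands.

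- **Baseline WPAI blanks.** A reader might infer that they do as much harm as visit-9 blanks, since the recorded change can be just as large in the other direction. But 13.2.5 takes over the primary model, which adjusts for baseline, and a baseline blank precedes treatment. Step 5 shows no loss from imputing.
- **EQ-5D-5L.** Five dimension comparisons plus two WPAI outcomes make seven single-item comparisons, and a reader might infer that all seven can receive a best outcome. The SAP does not support that. For EQ-5D-5L the best value is used only at inclusion, where it blocks improvement instead of creating it. It is also correct for a patient who truly was at Level 1.
- **Size.** The blank rates are assumed. The 9.4% type I error needs five times as many blanks on dupilumab as on placebo in a double-blind trial, and nothing in the SAP suggests such an imbalance.
- **Status.** Sections 6.2 and 13.2 make these analyses exploratory, with no claims intended and no multiplicity control.

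None of this answers the visit-9 WPAI rule. It applies as written, and it records the best possible outcome where none was observed.

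**Conclusion.** The point holds for WPAI at visit 9. One applicable blank among Q5, Q6 or Q2 is entered so as to give 0% on at least one separately analysed outcome. The rule and its effect on a patient's recorded value follow from the SAP alone. The size for the trial does not: the loss of about ten points of power (77% to 67%) rests on an assumed 10% blank rate in both arms and on assumed score distributions, and with few blanks the effect is small. No reading of the SAP shows that the WPAI result will be biased in favour of dupilumab; that would need unequal blank rates.

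The EQ-5D-5L part is separate and smaller. It concerns inclusion only, works against recording improvement, and has not been quantified. The primary analysis is unaffected. The WPAI rule should be corrected because it gives a wrong value and is cheap to change.

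**What to change.** In section 6.3.6:

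1. **WPAI.** Assess missingness per analysed outcome, and let this replace the form-level 25% exclusion. Otherwise blank Q2 and Q5 (33.3%) would still discard an observed Q6. At visit 9:
   - Q6 blank: activity impairment is missing.
   - Applicable Q5 blank: impairment while working and overall work impairment are missing.
   - Q2 blank: work time missed and overall work impairment are missing.
   - The patient's other observed WPAI outcomes are kept.
2. **Skips.** State that items skipped by design (not employed, or no hours worked) are not blanks.
3. **Remaining WPAI rules.** The baseline imputation may stay. Restate when the rules for items 1, 3 and 4 apply, since they now depend on the form-level count.
4. **EQ-5D-5L.** Do not set a dimension blank at inclusion to Level 1; treat it as missing for that dimension's comparison. Leave the overall summary missing only when the observed dimensions do not already settle it. Worsening on any observed dimension already means No improvement, and such patients should be kept.

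The cost is SAP wording and programming. The downside is slightly fewer patients in the affected outcomes.

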6.3.7. Handling of missing/incomplete dates for birthdate

If the entire date of birth is missing, no imputation is performed. Given that the data collection only involves the month and year of birth, any missing day is assumed to be the 1st.

6.3.8. Handling of missing/incomplete dates for diagnosis of CHE

If the entire date or the year of diagnostic is missing, no imputation is performed. In case of incomplete date with both missing day and month parts, missing day/month is imputed by January 1st. In case of incomplete date only for the day or month, the missing day or month is imputed by 1 representing the first day of the month or the first month of the year (January).

6.3.9. Handling of missing/incomplete dates for visit

If the entire date of visit is missing, no imputation is performed and the visit will be deemed not to have taken place. In case of incomplete date with missing year, day or/and month parts, missing year/day/month is not imputed and this date will be considered as unknown and outside the expected timeframe.

6.3.10. Handling of missing/incomplete dates for adverse events

In case of completely missing or incomplete AE onset date, an imputed AE onset date is calculated in order to derive AE treatment-emergence and AE period-occurrence statuses in any. Always one and the same imputation rule is used, that is, in order not to miss any AEs that occur or may have occurred from the first study treatment administration, imputation rule sets missing/incomplete onset date to the date of the first study treatment administration if another date is not obvious, otherwise "as early as possible" (see details below).

In case of completely missing or incomplete AE end date, an imputed AE end date is derived to help for imputation of missing/incomplete AE onset date, if any, so that inconsistency in the chronology of the dates does not arise (see details below).

Of note, imputed AE onset and end dates are for treatment-emergence/period-occurrence status categorization purpose only; they will neither be used to compute other information on AEs, such as duration, nor be displayed in any individual data listing.

Imputation of AE end date

For AEs that are not "ongoing", as reported by investigators on the adverse event forms, missing/incomplete end dates are handled as follows:

- In case of completely missing end date, missing end date is imputed by the date of the patient's end-of-study derived as the latest date among the date of premature withdrawal from study as reported in the "Early study discontinuation" eCRF form (if any) and the date of last study visit performed.
- In case of incomplete end date with both missing day and month parts, missing end day/month is imputed by 31 December.
- In case of incomplete end date with only missing day part, missing end day is imputed by the last day of the month.

Imputation of AE onset date

Missing/incomplete AE onset dates are handled as follows:

- In case of completely missing onset date:
 - o If AE end date (after being imputed as above where necessary) is after or equal to the date of the first study treatment administration, missing onset date is imputed by the date of the first study treatment administration.
 - If AE end date (after being imputed as above where necessary) is prior to the date of the first study treatment administration, missing onset date is imputed by the date of the patient's informed consent signature.
- In case of incomplete onset date with both missing day and month parts:
 - o If onset year is the same as the year of the first study treatment administration and AE end date (after being imputed as above where necessary) is after or equal to the date of the first study treatment administration, missing onset day/month is imputed by the day/month part of the first study treatment administration date.
 - o If onset year is the same as the year of the first study treatment administration and AE end date (after being imputed as above where necessary) is prior to the date of the first study treatment administration, missing onset day/month is imputed by 01 January.
 - o If onset year is prior to the year of the first study treatment administration, missing onset day/month is imputed by 01 January.
 - o If onset year is after the year of the first study treatment administration, missing onset day/month is imputed by 01 January.
- In case of incomplete onset date with only missing day part:
 - o If onset month/year is the same as the month/year of the first study treatment administration and AE end date (after being imputed as above where necessary) is after or equal to the date of the first study treatment administration, missing onset day is imputed by the day part of the first study treatment.
 - o If onset month/year is the same as the month/year of the first study treatment administration and AE end date (after being imputed as above where necessary) is prior to the date of the first study treatment administration, missing onset day is imputed by 01 (first day of the month).
 - o If onset month/year is prior to the month/year of the first study treatment administration, missing onset day is imputed by 01 (first day of the month).

o If onset month/year is after the month/year of the first study treatment administration, missing onset day is imputed by 01 (first day of the month).

6.3.11. Handling of missing/incomplete dates for medications

In case of completely missing or incomplete medication start date (respectively end date), an imputed medication start date (respectively end date) is calculated in order to derive a medication prior/concomitant status relative to study treatment in any case. Always one and the same imputation rule is used, that is, imputation rule considers medication as concomitant to study treatment as soon as the non-concomitance is not obvious, setting missing/incomplete start date to the date of the first study treatment administration if another date is not obvious, otherwise "as early as possible", and setting missing/incomplete end date to "as late as possible" (see details below).

Of note, imputed medication start and end dates are for categorization purpose only; they will neither be used to compute information on medications other than prior/concomitant status relative to study treatment, such as duration, nor be displayed in any individual data listing.

Imputation of medication end date

For medications that are not ticked "Ongoing", as reported by investigators on the concomitant medication forms, missing/incomplete end dates are handled as follows:

- In case of completely missing end date, missing end date is imputed by the date of the patient's end-of-study derived as the latest date among the date of premature withdrawal from study as reported in the "Early study discontinuation" eCRF form (if any) and the date of last study visit performed.
- In case of incomplete end date with both missing day and month parts, missing end day/month is imputed by 31 December.
- In case of incomplete end date with only missing day part, missing end day is imputed by the last day of the month.

Imputation of medication start date

Missing/incomplete medication start dates are handled as follows:

- In case of completely missing start date:
 - If medication end date (after being imputed as above where necessary) is after or equal to the date of the first study treatment administration, missing start date is imputed by the date of the first study treatment administration.
 - o If medication end date (after being imputed as above where necessary) is prior to the date of the first study treatment administration, missing start date is imputed by the date of the patient's informed consent signature.
- In case of incomplete start date with both missing day and month parts:
 - If start year is the same as the year of the first study treatment administration and medication end date (after being imputed as above where necessary) is after or equal to the date of the first study treatment administration, missing start day/month is imputed by the day/month part of the first study treatment administration date.
 - o If start year is the same as the year of the first study treatment administration and medication end date (after being imputed as above where necessary) is prior to the date of the first study treatment administration, missing start day/month is imputed by 01 January.
 - o If start year is after or prior to the year of the first study treatment administration, missing start day/month is imputed by 01 January.
- In case of incomplete start date with only missing day part:
 - o If start month/year is the same as the month/year of the first study treatment administration and medication end date (after being imputed as above where necessary) is after or equal to the date of the

first study treatment administration, missing start day is imputed by the day part of the first study treatment administration date.

- o If start month/year is the same as the month/year of the first study treatment administration and medication end date (after being imputed as above where necessary) is prior to the date of the first study treatment administration, missing start day is imputed by 01 (first day of the month).
- o If start month/year is after or prior to the month/year of the first study treatment administration, missing start day is imputed by 01 (first day of the month).

